Calibration of the sensor allows for accurate measurements. The output of the sensor is zeroed by immersing the sensor into a 0.9 percent saline bath which has been bubbled with nitrogen from a compressed nitrogen gas cylinder for at least 60 minutes. Though dissolving sodium sulfite would create a more stable zero oxygen solution, this method is not safe for measurements being done on the human cornea *in vivo*. Nitrogen purging is considered the most effective method to remove dissolved oxygen for the stated purpose (Butler IB, 1994). The gain of the sensor's output is adjusted after immersion in a second bath of 0.9 percent saline bubbled with room air to establish an oxygen tension of approximately 154.3 torr (or, 20.9% of the average barometric pressure less the partial pressure of humidity). The temperature of both baths is controlled at 35.9°C, the average human corneal temperature (Purslow C, 2005).

Corneal oxygen uptake rates are derived by rapid transfer of the sensor from the 154.3-torr bath to gentle contact with mild consistent pressure against the central cornea. This transfer takes less than 2 sec. There is an initial upward burst of the sensor output to approximately 160 torr, after which the partial pressure of oxygen falls monotonically as the cornea depletes oxygen from the reservoir of the sensor (i.e., oxygen dissolved in the polyethylene jacket). Contact with the normal open-eye cornea is discontinued within approximately 28-40 seconds—when the cornea has depleted the oxygen reservoir below 40 torr. The corneal oxygen uptake rate is defined in mmHg/sec as the average depletion rate over the 100-mmHg range from 140 to 40 mmHg. It is important to note this difference in units (torr vs. mmHg) is negligible as one torr is equivalent to 0.999998575337 mmHg. The resting oxygen uptake rate of the normal open-eye human cornea measured in this manner will therefore vary from 3.5 to 4.5 mmHg/sec.

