The low tear interchange rate reported by Polse suggests that if corneal edema is to be prevented with contact lens wear, the material must have high enough oxygen transmissibility to meet the oxygen needs of the cornea. This observation is consistent with the predictions by Fatt and Lin (Fatt I L. D., 1976) and Fatt and Hill (Fatt I H. R., 1970), who have shown that the contribution of tear flow to the oxygen tension at the anterior cornea for most low Dk/t hydrogel lenses would be as low as 4 mmHg. Many currently used hydrogel contact lenses can only supply adequate oxygen to the cornea directly by diffusion if the lens thickness is less than 0.10 mm (Decker M, 1978).

Study Objective

- I. Evaluate corneal oxygen uptake of a new translating contact lens design with comparison to published data and commercially available designs.
- II. Evaluate subjectively reported comfort of a new translating contact lens design with comparison to commercially available designs.

[figure not shown]
Hypothesis

We hypothesize that the Apioc lens design will provide greater tear exchange behind this novel soft contact lens than a standard soft contact lens. Its patented design suspends the lens from the upper eyelid thus allowing a looser fit and greater movement of the contact lens over the ocular surface than standard thickness soft contact lenses. These design aspects should lead to an increase in tear exchange behind the contact lens. Because tear exchange behind a soft contact lens is very difficult to measure on the human eye, and there is no tear exchange rate benchmark that is correlated with direct clinical benefits, the impact of the Apioc contact lens design will be assessed indirectly by measuring corneal oxygen uptake, as the cornea receives its oxygenation through the tears. Thus, our experimental hypothesis is that the cornea wearing the Apioc contact lens will have an oxygen uptake rate of ≥ 10 mm Hg.

Apioc is manufactured in Definitive 74 contact lens material (Dk/t = 44) (Benjamin, 2018). If the Apioc contact lens and standard contact lens have center thickness of 0.20 mm, then the Dk/t of the lenses is 22 which correlates with 9 percent EOP. If the Apioc lens movement with blinking at a normal blink rate allows greater oxygen delivery by 30 percent to 12 percent EOP, (See illustration by Benjamin below) it will allow normal corneal thickness, (prohibit corneal swelling) in daily wear. This provides a clinical benchmark demonstrating

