that the Apioc contact lens design will provide an improvement in corneal physiology over the standard soft contact lens design.

Note, lenses having an Equivalent Oxygen Percentage (EOP) of 9.9%, do not induce corneal edema. Holden and Mertz (Holden BA, 1984) state an oxygen transmissibility of at least $24.1 \pm 2.7 \times 10^9$ (cm X ml C>2)/(sec X ml X mmHg) which correlates closely with Benjamin, above.

Study Lenses

The Apioc contact lens is a daily wear soft contact lens, which is classified under 21 CFR 886.5925 (product code: LPL). The FDA has previously made risk determinations (class II, non-significant risk) for devices classified under 21 CFR 886.5925. The Apioc-A contact lens has the same actions and indications for use as other contact lenses classified under 21 CFR 886.5925. As a non-significant risk device, the Apioc contact lens is exempt from the IDE regulation (21 CFR 812).

Subject Qualification

Number of Subjects

The total number of enrolled subjects will be 10. This is a common sample size for corneal oxygen uptake studies.

Inclusion Criteria

Prior to enrollment in the study, the following criteria must be met by each prospective subject:

1. Provide informed consent.
2. Appear willing and able to adhere to instructions set forth in the protocol.
3. Be between the ages of 18 and 45.
4. Be an experienced contact lens wearer.
5. Be an eyecare clinician or clinician-in-training.
6. Flat and steep keratometry readings within 40 to 50D.
7. Clear, healthy corneas with no irregular astigmatism.
8. Normal, healthy conjunctiva in both eyes.
9. Be able to provide corneal topography measurements.
10. Be able to provide manifest refraction measurements.

Exclusion Criteria

1. Irregular corneal astigmatism.
2. Use of topical or systemic antihistamines within the previous week.
3. Use of topical ophthalmic drops within the previous two days.
4. History of corneal surgery.
5. Currently pregnant or lactating.
6. Systemic disease that would interfere with contact lens wear.
7. Previous diagnosis of dry eye syndrome.

Study Design and Procedures

Study Design

Structure: Single center, serially recruited

Duration: approximately one month from consent to study completion

Visit Schedule: up to three study visits separated by a minimum of 48 hours

Clinical Study Methods

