 - B. Low oxygen conditions: close both eyes for 5 minutes prior to testing
 - C. Soft contact lens conditions: apply contact lens to test eye and wait at least 5 minutes. Blink to a metronome set at 15 blinks per minute. Remove the contact lens immediately before the probe is applied in step IV below. In one visit, measure up to three different contact lens designs in a randomized order:
 - i. Apioc lens design with lenticular
 - ii. Apioc lens design without lenticular
 - iii. Standard lens design with a thickness equivalent to the mean thickness of the Apioc design with lenticular
 - iv. Commercially available contact lenses
- IV. Collect measurements in accordance with the procedure manual.
 - A. Measurements will be randomized to minimize bias.
 - B. Measurements will be repeated if initial review of data indicates poor quality.
- V. Determine whether the study visit is complete.
 - A. Visually assess conjunctival redness. An increase of two grades in bulbar or limbal redness on the reference grading scales indicates the current study visit is complete.
 - B. Ask the subject to complete the comfort assessment (see Appendix). An answer of “no” to question 2 indicates the current study visit is complete.
 - C. A completion of all measurements listed in the conditions above (A, B, and up to three contact lenses for condition C) indicates the current study visit is complete.
- VI. If another measurement will be collected in the current study visit, a rest period of at least ten minutes of normal open eye blinking will be allowed between measurements of the same eye.

Concluding Visual and Ocular Assessment

- I. Measure visual acuities with presenting correction in place: OD, OS
- II. Anterior segment slit lamp examination
 - A. Ocular abnormalities noted

Corneal Oxygen Uptake Calculation

Calculate the slope over a 100 torr drop in oxygen uptake – from 140 torr to 40 torr.

Data Analysis

The study objective is to compare the corneal oxygen uptake rates of the standard conditions (normal open and closed eyes) and test conditions. Paired t-tests will be performed to determine if this objective is met.

The individual performing data analysis will be masked to minimize bias.

Safety and Adverse Events

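### The paired t-tests are tied to open and closed eyes versus test conditions; no Apioc-versus-lens contrast is specified, and the ≥ 10 mm Hg hypothesis has neither a test nor the outcome's unit

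*Combined protocol and SAP*

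**What the plan says.** The only testing plan is in Data Analysis. It states the objective, "The study objective is to compare the corneal oxygen uptake rates of the standard conditions (normal open and closed eyes) and test conditions", and adds: "Paired t-tests will be performed to determine if this objective is met". The same objective sentence closes the measurement part of Background and Introduction. Apart from this, the documents give only the slope calculation and the masking of the analyst.

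The aims elsewhere are different:

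- Study Objective I evaluates uptake of the new design "with comparison to published data and commercially available designs".
- Hypothesis proposes that "the Apioc lens design will provide greater tear exchange behind this novel soft contact lens than a standard soft contact lens". It expects its benchmark to demonstrate "that the Apioc contact lens design will provide an improvement in corneal physiology over the standard soft contact lens design".
- Hypothesis also sets a numerical target: "our experimental hypothesis is that the cornea wearing the Apioc contact lens will have an oxygen uptake rate of ≥ 10 mm Hg".

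On the outcome itself, Background and Introduction says: "The corneal oxygen uptake rate is defined in mmHg/sec as the average depletion rate over the 100-mmHg range from 140 to 40 mmHg". The resting open-eye rate is expected to "vary from 3.5 to 4.5 mmHg/sec". The same section says that eye closure and lens wear reduce the oxygen available and so raise uptake above the resting rate, by an amount related to how far oxygen falls.

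Oxygen Consumption of the Cornea Measurement lists four lens types: Apioc with lenticular, Apioc without lenticular, a standard lens matched in thickness to the mean of the version with lenticular, and commercial lenses. At most three are measured per visit. The lens options in Clinical Study Methods do not mention the standard lens.

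**The concern.** The study wants to say that Apioc is better than a standard soft lens. The comparisons it specifies are between eye states and test conditions. The bracket in the objective defines the standard conditions as open and closed eyes, so the phrase cannot be read as the standard lens.

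If the plan is followed as written, the comparative claim rests on no named test. With two Apioc versions, two kinds of comparator and repeat visits, the contrast could be chosen after the data are seen. There is also a temptation to compare the separate p-values of each lens against an eye state, which does not test the lens difference.

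The one numerical hypothesis cannot be assessed at all until its unit, scale and direction are settled. A paired test between two conditions does not test one condition against a fixed value.

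**Working it through.** **1. Questions against planned tests**

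| Question | Section | Contrast specified in Data Analysis? |
|---|---|---|
| Eye states vs test conditions | Background; Data Analysis | Yes |
| Apioc vs standard lens | Hypothesis | No |
| Apioc vs commercial lens | Study Objective I | No |
| Apioc rate vs 10 | Hypothesis | No |

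Two eye states by up to four lens types gives up to 2 × 4 = 8 paired tests under the stated objective. None is lens against lens.

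**2. The plan's own figure.** The sample size of 10 (Number of Subjects) is justified by custom. No alpha, sidedness, power, effect size or SD is given, so it cannot be reproduced. Steps 3 and 4 therefore use assumed units.

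**3. What the planned tests can show.** Assumptions: n = 10; two-sided 5%; equal independent normal errors with SD 1/√2 per condition, so each paired difference has SD 1; open eye at 0; 200,000 simulated trials per setting.

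- *Open-eye tests.* Both lens-versus-open-eye tests are significant in over 99.9% of trials when the lenses are equal (both at 2 SD). The result is the same when they differ (standard 3, Apioc 2). The outcome does not depend on the lens difference.
- *Direct paired lens test.* It is significant in 5% of trials when the lenses are equal and in 80% when they differ by 1 SD.
- *Closed-eye tests, standard 3 and Apioc 2.* With the closed eye at 3, they are significant in 80% (Apioc) and 5% (standard). With it at 4: over 99.9% and 80%. With it at 5: over 99.9% for both. They can respond to a lens difference, but how much depends on where the closed eye lies, which the documents do not give.
- *Direction of disagreement, closed eye at 4.* With both lenses at 3, only the Apioc test is significant in 11.8% of trials and only the standard-lens test in 11.7%. With standard 3 and Apioc 2, the figures are 19.6% and under 0.01%. The direction carries information, but it is not an estimate of the difference.

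**4. Precision of the direct contrast.** Power comes from the noncentral t distribution with n − 1 degrees of freedom and noncentrality d√n. The 95% CI half-width is t(0.975, n − 1)/√n, in SDs of the paired difference.

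- 10 pairs, d = 1.0: noncentrality √10 = 3.16; power 80%; half-width 2.262/√10 = 0.72 SD.
- 8 pairs (assumed), d = 1.0: noncentrality √8 = 2.83; power 68%; half-width 2.365/√8 = 0.84 SD.

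**5. The threshold.** Hypothesis gives mm Hg; the outcome is in mmHg/sec. There are three possible readings:

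- *A rate in mmHg/sec.* 10/4.5 = 2.2 and 10/3.5 = 2.9 times the resting open-eye rate. Under the Background's rule that less oxygen gives higher uptake, ≥ points to a worse-supplied cornea.
- *An oxygen tension.* The number resembles the 5 to 10 mmHg attributed to tear pumping in Tear Flow Under Hydrogel Contact Lenses. Tension under the lens is not the defined outcome.
- *An equivalent oxygen percentage (EOP).* Hypothesis uses 9 percent rising to 12 percent, and 9.9% as a level without edema. A value near 10 with ≥ as the favourable direction would fit, but EOP is not the defined outcome and no conversion from the measured rate is given.

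**6. Availability of pairs.** At most three of four lens types are measured per visit, a visit can end before all conditions are done, and one of the two lens lists does not mention the standard lens. An Apioc-standard pair is therefore not guaranteed at each visit. Later visits may recover some pairs. The documents do not allow the number missing to be estimated.

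**The case against.** The strongest reply is that Data Analysis says only that paired t-tests will be done and does not list contrasts. The standard and commercial lenses are among the conditions to be measured, the design is within-subject, and a paired t-test suits a lens comparison. That stands in part. A reader might infer that the plan excludes the lens comparison or that its data could not support it. The documents do not say so. The gap is mainly one of pre-specification: the tests are attached to an objective defined by eye states, and no lens contrast is named.

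Three other strong readings also go too far:

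- *That closed-eye tests say nothing about the lenses.* In the illustration they respond in some settings, and the direction of disagreement is informative.
- *That the threshold is simply reversed, or that EOP was plainly meant.* The text says uptake rate and mm Hg, which fits neither a rate nor EOP cleanly. The documents do not settle which was intended.
- *That a known share of pairs will be lost.* An early stop ends only that visit. Clinical Study Methods repeats the measurements at two further visits, while Study Design allows up to three visits in all. Lens allocation may also be set out in the procedure manual, which is not among the documents.

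It is also fair to say that Objective I names commercial designs and published data, not the standard lens. Making the standard lens primary rests on the Hypothesis section. It is a defensible choice, not the only one.

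**Conclusion.** The concern holds and must be fixed before data are analysed. Data Analysis specifies no Apioc-versus-standard or Apioc-versus-commercial contrast, although the intended conclusion and Objective I depend on them. Open-eye contrasts cannot show which lens is better; closed-eye contrasts can respond to a lens difference but neither estimate nor directly test it. The ≥ 10 mm Hg hypothesis has no planned test and does not match the defined outcome.

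These conclusions rest on the text. The only figure drawn from the documents alone is the 2.2 to 2.9 ratio, which applies if the threshold is read as a rate. The simulated percentages and power figures rest on the assumed SD units, positions and 5% level. They show why a direct contrast is better, not how much harm this trial would suffer. No number is claimed for missing pairs.

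**What to change.** **Data Analysis**

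- Name as primary the within-subject paired t-test, with 95% CI, of Apioc minus the standard lens in mmHg/sec. Name the Apioc version in advance. Call the contrast thickness-matched only if that version is the one with lenticular.
- State that a negative difference favours Apioc.
- Use each subject's mean over the visits at which both lenses were measured, and report the number of complete pairs.
- Add Apioc minus a commercial lens as a named secondary contrast for Objective I. Leave the comparison with published data descriptive.
- Keep the open-eye and closed-eye contrasts as validity checks.

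**Hypothesis**

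- Reconcile the unit, scale and direction of ≥ 10 mm Hg with the outcome definition, the oxygen tensions and the EOP benchmarks.
- If a rate is meant, report Apioc's mean rate with 95% CI against the corrected value.
- If EOP or tension is meant, state the conversion from the measured rate or withdraw the threshold.

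**Clinical Study Methods and Oxygen Consumption of the Cornea Measurement**

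- Reconcile the two lens lists.
- Require the two lenses of the primary contrast at each visit, in randomised order and within the existing maximum of three. Leave the third slot to the sponsor.

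**Cost.** The change is to wording and lens allocation. It adds no subjects and does not raise the maximum of three lenses per visit, although two slots that are now optional become required. The third slot must be shared between the commercial lens and the other Apioc version, so those are measured less often and the secondary contrast will be less precise. Pairs can still be lost when a visit ends early.

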In this study, an experienced clinician will apply the oxygen electrode as described above to one eye of up to 10 subjects who are experienced contact lens wearers, eyecare clinicians or clinicians-in-training, and have no active ocular conditions that would preclude short term contact lens wear.

There will be up to five scenarios that will be examined at each visit: cornea with no stimulus to represents the high oxygen condition; immediately after gently closing their eyes for 5 minutes to represent the low oxygen condition; and after contact lens wear. Lens options include Apioc lens design with lenticular, Apioc lens design without lenticular, and commercially available contact lenses. The contact lens conditions will be worn with normal blinking – every four seconds for five minutes prior to oxygen uptake measures. The scenarios will be randomized to minimize bias.

Each of these measurements lasts less than one minute and are repeated at two additional visits.

A rest period of at least ten minutes of normal open eye blinking should be allowed between measurements of the same eye.

The conjunctiva of the subject will be examined prior to probe applications and between probe applications to assess ocular irritation induced by the probe. An increase in two grades on to the Brien Holden Vision Institute Grading Scales (see appendix) will indicate a need to discontinue measurements for the day.

Screening

- I. Statement of Informed Consent
 - A. Prior to enrollment, each subject must read, understand, and sign the informed consent document. It must also be signed by a study team member who is authorized to consent subjects.
 - B. Each subject must be given a signed version of this document.
- II. Eligibility
 - A. All criteria must be met.
 - B. All responses to Inclusion Criteria must be “yes.”
 - C. All responses to Exclusion Criteria must be “no.”

III. Demographics – Age (in years and months)

Baseline Visual and Ocular Assessment

- I. Measure presenting visual acuities: OD, OS
- II. Anterior segment slit lamp examination
 - A. Ocular abnormalities noted
 - B. Eligibility – examiner will determine if subject continues to meet inclusion/exclusion criteria

Oxygen Consumption of the Cornea Measurement

- I. Setup equipment in accordance with the procedure manual.
- II. Instill 1 drop of artificial tears into the eye that will not be measured.
- III. Experimental Conditions
 - A. High oxygen conditions: normal open eye conditions with normal blinking

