Appendix

Comfort Assessment

1. Please make a mark on the line to tell us your answer. How much discomfort did you feel with the contact lens on your eyes?

N/A

2. Please circle your answer. Subjectively, do you feel comfortable doing another measurement today?

Yes

No

Brien Holden Vision Institute Grading Scales

**BRIEN HOLDEN®
VISION INSTITUTE**

GRADING SCALES*

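### Only the data analyst is masked, which leaves the subject-rated comfort comparison (Objective II) open to expectation bias

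*Combined protocol and SAP*

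**What the plan says.** Under Study Objective, item II is to "Evaluate subjectively reported comfort of a new translating contact lens design with comparison to commercially available designs". The measure is question 1 of the Comfort Assessment in the Appendix, where the subject marks a line in answer to "How much discomfort did you feel with the contact lens on your eyes". The subject completes it during the visit, at step V.B of Oxygen Consumption of the Cornea Measurement.

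Two of the Inclusion Criteria describe the raters: "Be an experienced contact lens wearer" and "Be an eyecare clinician or clinician-in-training".

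On control of bias, Data Analysis states "The individual performing data analysis will be masked to minimize bias". Clinical Study Methods and the measurement procedure add that the order of scenarios and measurements is randomised. There is no other statement on masking.

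On lens handling, step III.C says "apply contact lens to test eye and wait at least 5 minutes", and that the lens comes off just before the probe goes on. It does not say who applies or removes it. Clinical Study Methods says that "an experienced clinician will apply the oxygen electrode as described above to one eye" of each subject; no other staff role in the measurement is described.

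**The concern.** Masking the analyst guards against choices made after the data exist. A comfort rating is fixed when the subject marks the line, so a preference for or against the new design has already entered the data before the analyst sees them.

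The raters are not naive. Clinicians and trainees who also wear lenses are likely to recognise that one design is novel and to have an opinion about it. If they know which lens is on, a real comfort difference and a difference produced by expectation cannot be told apart. The comparative part of Objective II would then be hard to interpret, whichever way the result fell.

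**Working it through.** The plan states no figure on this point, so the check is to set each bias control beside the outcome it would have to protect.

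1. **Outcomes.** Objective I is corneal oxygen uptake, a slope read from a sensor. Objective II is comfort, a mark made by the subject. The first is instrument-read; the second is a judgement.

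2. **Analyst masking (Data Analysis).** This protects decisions made during analysis. For Objective II the judgement is made earlier, at step V.B, by the subject. The control does not reach it.

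3. **Randomised order (Clinical Study Methods; step III.C and step IV.A).** This balances order and carry-over effects across designs. It determines when each lens is worn, not whether the subject knows which one it is. The control does not reach lens identity.

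4. **Subject masking.** None is stated. Step III.C, where lenses are presented, does not mention labels, containers, disclosure or the person handling the lens. The comfort form in the Appendix gives no rule on how the lens is to be identified.

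5. **What the subject could learn unaided.** Under Hypothesis, the Apioc lens is described as hanging from the upper lid, fitting more loosely and moving more than a standard soft lens. An experienced wearer might detect that. Step III.C, however, lists four lens options: Apioc with lenticular, Apioc without lenticular, a standard lens matched to Apioc's average thickness, and marketed lenses. Up to three are worn in a visit. Feeling that two lenses differ is not the same as being told which one is the sponsor's.

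Taken together, neither of the two stated controls acts on the route from knowledge of the lens to the comfort mark, and no third control is stated.

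**The case against.** The strongest reply is that this rests on silence. The protocol never says that subjects are told which lens they wear. It also refers to a procedure manual for setup and measurement that is not among the documents, so masking steps could be there. This stands as a limit. A reader might infer that the study is open-label for comfort by design; the text supports only that nothing in the protocol prevents it.

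A second reply is that masking may fail, because experienced wearers could recognise a lens that hangs from the lid and moves more. This stands in part. It means masking may be incomplete, and it is why a fallback is needed. It does not show that withholding the design's identity is worthless.

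A third reply is that comfort has no planned analysis: the paired t-tests under Data Analysis are assigned to oxygen uptake. That is true and is a separate gap. Comfort remains a stated comparative objective, and no later analysis can remove bias already in the ratings.

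Three stronger readings are tempting and should not be drawn:

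- **That subjects can be masked with no additional staff.** The documents do not say who applies or removes lenses, or who is present, so this cannot be shown.
- **That the bias has a known size relative to what 10 subjects can detect.** No standard deviation, significance level or comfort test is given, so any such figure would be an assumption set against an analysis the plan does not contain.
- **That question 2 of the comfort form, where a negative answer ends the visit, carries the bias into the oxygen data.** That question asks about willingness to have another measurement; it is not a lens rating. The documents give no reason to think lens identity drives the answer.

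**Conclusion.** The concern holds for Objective II. The protocol masks only the analyst, the comfort comparison depends on ratings by clinician subjects who may know the design, and neither stated bias control addresses this. The size and direction of any bias cannot be derived from the documents.

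The conclusion assumes that the procedure manual does not already conceal lens identity from subjects. If it does, a sentence in the protocol saying so would settle the point. No effect on the instrument-read oxygen uptake outcome is claimed.

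This is more than a missing detail, because a modest change in how lenses are presented would reduce the bias. It should be made, with the expectation that masking may be partial.

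**What to change.** In step III.C of Oxygen Consumption of the Cornea Measurement:

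- Present lenses from coded containers in the randomised order.
- Do not tell the subject which design is worn.
- State who applies and who removes each lens, and how the subject's view of it is limited.

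On the Comfort Assessment form, record only the lens code. Leave the probe operator unmasked.

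In Data Analysis, extend the masking statement to say whether subjects are masked to lens design. Where masking is not feasible for a design, say so and report comfort as an open-label outcome.

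**Cost.** Coded labels, a key kept from the subject, and a few sentences of protocol text. Masking the analyst presumably already requires some coding of conditions, although the protocol does not describe it. Whether another person is needed depends on who handles the lenses, which has to be specified first. The oxygen measurement itself does not change. The main drawback is that subjects may still feel or see the difference, so the comfort results would need to be read with that in mind.
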